1 STUDY SYNOPSIS

Protocol Title	Study to evaluate the Efficacy and Safety of CardiolRx™ in Patients with COVID-19 and Cardiovascular Disease or Risk Factors A double-blind, placebo-controlled Phase II/III Study (LANCER)
Diagnosis	Non-critical patients, hospitalized for COVID-19 with a prior history of cardiovascular disease (CVD) and/or at least one risk factor for CVD
Inclusion Criteria	
 1. Males and females 18 years of age or older 2. Hospitalized for COVID-19 with most recent test positive*; not receiving, or likely to receive invasive mechanical ventilation within the next 24 hours 3. Prior history of at least one of: 
 i) CVD [cardiovascular (CV), cerebrovascular or peripheral vascular diagnoses], ii) Age > 64, iii) Diabetes (DM), iv) Hypertension (HTN), v) Abnormal serum lipids, vi) Obesity (BMI\geq30 or waist circumference >102 cm [40"] for men and >88 cm [35"] for women), vii) Current smoker
	* Must be polymerase chain reaction (PCR) test.
Exclusion Criteria	
 1. Patients who have received vasopressors, extracorporeal membrane oxygenation and mechanical ventilation within last 30 days 2. Background of cardiac transplant surgery 3. Implanted defibrillator (ICD) in the last month 4. Implanted left-ventricular assist device (LVAD) 5. Acute coronary syndrome (ACS) within 30 days 6. Percutaneous coronary intervention (PCI) within 30 days 7. Receiving any immuno-suppressive agent other than dexamethasone 8. History of QTc interval prolongation 9. QTc interval > 500 msec (see section 9.2.3 for bundle branch block [BBB] correction)

10. Treated with strong inducers of CYP3A4 or CYP2C19, as listed in Appendix 17.7
11. Chronic renal failure, determined as eGFR < 30 ml/min
12. Elevated alanine aminotransferase (ALT) or aspartate aminotransferase (AST) > 5 times the upper limit of normal (ULN) or ALT or AST >3x ULN plus bilirubin >2x ULN
13. Bacterial sepsis, defined as documented bacteremia at the time of presentation or other active bacterial infection
14. Current participation in any research study involving investigational drugs or devices with the exception of dexamethasone, remdesivir, Baricitinib plus remdesivir as well as convalescent plasma and monoclonal antibodies, or any other therapy approved under emergency use in the region for treatment of COVID-19
15. Inability or unwillingness to give informed consent
16. Ongoing drug, alcohol or cannabis abuse
17. Women who are pregnant or breastfeeding
18. Any factor, which would make it unlikely that the patient can comply with the study procedures
19. Hemoglobin <8.5 gm/dL
20. Leukocyte count < 3000/ mm³
21. Platelets < 100,000 / mm³
22. Current diagnosis of cancer, with the exception of non-melanoma skin cancer
23. Showing suicidal tendency as per the Columbia-Suicide Severity Rating Scale (C-SSRS) administered at screening
24. Any cannabinoid intake in the past month
25. Body weight > 170 kg

Primary Efficacy Objective

The primary objective of this study is to evaluate the effect of CardiolRx™ on prevention of cardiovascular and COVID-19 complications in patients hospitalized for COVID-19.

Primary Efficacy Endpoint

The primary composite endpoint in this study is to experience one of the following events during the first 28 days post randomization:

- All-cause mortality
- Requirement for ICU admission and/or ventilatory support due to COVID-19
- CV complications*:
 - heart failure (HF) or
 - Acute myocardial infarction (AMI) or

PROPRIETARY AND CONFIDENTIAL

- myocarditis or
- new sustained or symptomatic arrhythmia or
- stroke

*see Appendix 17.8 for definitions

**Secondary Efficacy
Endpoints**

- ...Win Ratio of Ordinal Outcome Scale endpoint:
 - 1) not hospitalized and no limitations of activities;
 - 2) not hospitalized, with limitation of activities, home oxygen requirement, or both;
 - 3) hospitalized, not requiring supplemental oxygen and no longer requiring ongoing medical care
 - 4) hospitalized, not requiring supplemental oxygen but requiring ongoing medical care
 - 5) hospitalized, requiring any supplemental oxygen;
 - 6) hospitalized, requiring noninvasive ventilation or use of high-flow oxygen devices;
 - 7) hospitalized, receiving invasive mechanical ventilation or extracorporeal membrane oxygenation (ECMO);
 - 8) MI or stroke diagnosed since randomization
 - 9) death.
- Change in hs-troponin from baseline to peak elevation during the 28-day treatment period
- Change in TNF-alpha from baseline to peak elevation during the 28-day treatment period

Other Endpoints

- Percentage of patients developing any of the primary endpoint components within 60 days post randomization
- CV mortality at 28 days post randomization
- Percentage of patients requiring dialysis within 28 days post randomization
- Win ratio of the Ordinal Outcome Scale endpoint within 60 days of randomization
- Patient Impression of Change Questionnaire (PICQ) at Day 28 and at Day 60
- Development of severe lymphopenia, defined as < 1000 cells/microliter within 28 days post randomization
- Change in (elevation of) hs-troponin, NT-proBNP, D-dimer and in inflammatory markers (hs-CRP, ferritin, TNF-alpha, IL-1 beta, IL-6, IL-10) from baseline to Day 7 [area under the curve (AUC)]
- Change from baseline to peak elevation of NT-proBNP, D-dimer and in inflammatory markers (hs-CRP, ferritin, TNF-alpha, IL-1 beta, IL-6, IL-10) during the 28-day treatment period
- Change from baseline to peak elevation of lactate dehydrogenase (LDH) during the 28-day treatment period
- Difference in cardiac magnetic resonance imaging (CMR) parameters between the two treatment groups after 4 weeks of study treatment (subset of patients at selected sites)

Primary Safety Objective

To evaluate the safety of CardiolRx™ in patients with COVID-19 infection

Primary Safety Endpoint

Number of serious adverse events (SAEs) and adverse events (AEs) during the 60-day study period in each group

Secondary Safety Endpoints:

Changes in C-SSRS, blood chemistry and hematology parameters (including lymphocyte count), ALT, AST, bilirubin, eGFR, creatinine, international normalized ratio (INR) as well as QTc interval

Number of Patients:

422 patients will be randomized (211 to CardiolRx™ and 211 to placebo)

Scheduled Duration of Study:

Estimated 9 months recruitment, 2 months follow-up, data cleaning 2 months and 2 months statistical analysis and reporting;

If all timelines are met, the total duration of the study will be approx. 15 months.

Design & Methodology

Multi-center, double-blind, randomized, placebo-controlled, parallel group design. 1:1 randomization.

Screening (Day 0-1): Patients hospitalized for COVID-19 will be screened. If patient consent can be obtained, baseline assessments will be carried out: Physical examination (including vital signs),

electrocardiogram (ECG) including QTc interval assessment, echocardiogram to measure left-ventricular ejection fraction (LVEF), chest X-ray, local laboratory (including complete blood count [CBC], Alanine aminotransferase [ALT]/ Aspartate aminotransferase [AST], alkaline phosphatase, bilirubin, creatinine/ estimated Glomerular filtration rate [eGFR], international normalized ratio [INR], serum pregnancy test [in women with child-bearing potential only], glucose, total cholesterol, lymphocyte count and lactate dehydrogenase [LDH]. A Columbia-Suicide severity rating scale (C-SSRS will also be completed). Frozen samples will be retained for central analysis of CardiolRx™ levels, high sensitivity troponin (hs-troponin), N-terminal pro b-type natriuretic peptide (NT-proBNP), D-dimer as well as inflammatory markers (high sensitivity C-reactive protein [hs-CRP], ferritin, tumor necrosis factor [TNF]-alpha, interleukin [IL]-1 beta, IL-6, IL-10).

If all eligibility criteria are met, the patient will be randomized to either CardiolRx™ or placebo. Randomization must be no later than 96 hours after hospital admission. Patients awaiting planned admission to hospital in an emergency room for less than 96 hours can be screened and enrolled into the trial.

Study treatment will be initiated in the evening of Day 1 after all baseline assessments have been completed and the patient is randomized.

Oral administration is as follows:

Study Day	a.m. dose [mg/kg of body weight] CardiolRx™ or placebo	p.m. dose [mg/kg of body weight] CardiolRx™ or placebo
1	N/A	2.5
2	2.5	2.5
3	2.5	5
4	5	5
5	5	7.5
6 - 28	7.5	7.5

Study medication must be taken with food.

If the next higher dose is not tolerated, the dose will be reduced to the previous tolerated dose. The highest tolerated dose will be administered until Day 28.

On Days 3, 5, and 7, an ECG will be recorded 5 hours post morning dose (time window 3.5 – 6 hours) with QTc intervals measured. If the QTc interval is >500 msec or an increase of > 60 msec from baseline is observed, the study medication must be stopped immediately.

In addition to prolongation of the QTc intervals, careful observation is required to detect other Adverse Drug Reactions (ADRs) and Drug-Drug Interactions (DDIs). Because CardiolRx™ may inhibit the metabolism of other drugs, new symptoms may represent toxicity from a concomitant medication that had previously been well tolerated. For more detailed discussion, see the Investigational Brochure (IB), section 6.3.

If the patient is discharged before Day 7, the assessments up to Day 7 will be carried out as out-patients or home visits. After Day 7, all remaining scheduled assessments will be carried out during out-patient visits.

After Day 7, assessments will be carried out on a weekly basis until Day 28.

Frozen samples will be retained for central analysis of CardiolRx™ levels, hs-troponin, NT-proBNP, D-dimer, inflammatory markers (hs-CRP, ferritin, TNF-alpha, IL-1 beta, IL-6, IL-10) and additional parameters of interest every two days until Day 7 as well as on Day 28.

The assessments on Day 28 include the following: Physical examination (including vital signs), ECG recorded 5 hours post morning dose (time window 3.5 – 6 hours) for measurement of QTc interval, echocardiogram to measure LVEF, chest X-ray, local and central laboratory assessments. In addition, a C-SSRS will be completed and the patient will be asked to answer a PICQ. In a subset of patients at selected sites, a CMR assessment will be done as well (this will be scheduled for day 45 if not possible to obtain on day 28).

Further follow-up visits are scheduled for Day 45 and Day 60 post randomization. These include a clinical assessment (including vital signs) as well as the completion of the PICQ (PICQ on Day 60 only). Any changes in concomitant medications and (S)AEs will also be recorded.

Information regarding the Ordinal Outcome Scale will be collected at each visit.

Concomitant Treatments

Patients may be on standard of care (SOC) treatment(s) for all current conditions, as prescribed by their treating physician, including dexamethasone, remdesivir, baricitinib plus remdesivir, intravenous monoclonal antibody infusion (administered prior to admission), and convalescent plasma therapy, with the exception of cannabinoids and strong inducers of CYP3A4 and CYP2C19 (see Appendix 17.7).

Data Safety and Monitoring

The QTc intervals for the first 100 patients will be reviewed by the Data Safety and Monitoring Committee (DSMC) in an unblinded fashion. If QTc interval prolongation occurs more often in the active group, as compared to placebo, the DSMC will continue close monitoring of the QTc intervals.

The DSMC will also review all safety events on an ongoing basis by treatment code and will conduct a formal (unblinded) interim analysis after approximately 50% of the patients have completed 28 days of study or terminated the study earlier, and will make recommendations to the Steering Committee on further conduct of the study following Stopping Guidelines in section 11.7 of this protocol.

In addition, the DSMC has the right to recommend stopping the trial early for evidence of harm that was not pre-defined by a formal stopping rule.

Sample Size Estimation

Assuming that 19% of patients qualifying for the study in the placebo group would develop one or more primary outcomes, a treatment effect of lowering the event rate by 50% (i.e. only 9.5% of patients treated with CardiolRx™ would experience CV or COVID-19 complications), a two-sided alpha of 0.05 and 80% power, 211 patients per group (422 in total) would be required.

Consideration will be given to adjust the sample size just before the formal interim analysis is carried out, should the observed event rate differ from the assumption above. Consideration will also be given to upgrading the Ordinal Outcome Scale first secondary endpoint to be the primary endpoint should the event rate of the current primary endpoint be significantly lower than the above assumption. This would be carried out in a blinded fashion. If the overall primary event rate is lower than $(19 + 9.5)/2 = 14.25\%$, the sample size will be increased to preserve 80% power to detect a 50% relative reduction with a two-sided alpha of 0.05.

Statistical Analysis Approach:

Primary efficacy analysis:

For the primary efficacy analysis, the proportions of subjects with at least one primary composite endpoint event will be compared using

Fisher's exact test. In addition, the 95% confidence interval for the proportion using exact (Clopper-Pearson) estimates will be provided. A secondary exploratory sensitivity analysis of the primary endpoint will compare time to the occurrence of the first primary event between the two groups using a Cox proportional hazards model. Kaplan-Meier plots for each treatment group will also be generated.

Secondary efficacy and safety analyses:

The first secondary efficacy analysis will be analyzed using the F-S test (Finkelstein and Schoenfeld 1999). This method compares each subject to every other subject in a pairwise manner following the ranking of the first secondary endpoint:

- 1) not hospitalized and no limitations of activities;
- 2) not hospitalized, with limitation of activities, home oxygen requirement, or both;
- 3) hospitalized, not requiring supplemental oxygen and no longer requiring ongoing medical care
- 4) hospitalized, not requiring supplemental oxygen but requiring ongoing medical care
- 5) hospitalized, requiring any supplemental oxygen;
- 6) hospitalized, requiring noninvasive ventilation or use of high-flow oxygen devices;
- 7) hospitalized, receiving invasive mechanical ventilation or extracorporeal membrane oxygenation (ECMO);
- 8) MI or stroke diagnosed since randomization
- 9) Death

The F-S test is based on the sum of 'scores' of subjects in the CardiolRx™ group. Where the score is 1, -1 or 0 according to whether the subject is the winner, the loser or tied, respectively, according to the hierarchy above.

In addition, the CardiolRx™ to placebo Win ratio (WR) will be calculated, as described by Pocock.(Pocock et al. 2012) For this statistic, every subject in the CardiolRx™ group is compared to every subject in the placebo group in a pairwise manner following the ranking of the first secondary efficacy endpoint. The WR is the number of pairs with CardiolRx™ subject 'wins' divided by the number of pairs with placebo subject 'wins'. The associated 95% CI will be based on the F-S test statistic to ensure consistency between the CI and the F-S test. A 95%CI for the WR entirely above 1 indicates a better outcome in the CardiolRx™ group.

Changes in hs-troponin and TNF-alpha to peak elevation from baseline during the 28-day treatment period will be compared using an ANCOVA with baseline as covariate.

To control the family-wise Type I error rate, the Benjamini-Hochberg procedure (Benjamini and Hochberg 1995) will be applied.

For the other efficacy endpoint analyses, see section 11.2.3 of this protocol.

Descriptive statistics will be used to compare baseline characteristics between the two groups. Continuous variables will be expressed as mean \pm standard deviation (SD) or as median and interquartile range (IQR); categorical variables will be expressed in counts with percentages.

The primary analyses will follow the intention-to-treat principle. Per-protocol secondary analyses may be considered, if appropriate.

Interim Analysis

A formal interim analysis will be carried out after approximately 50% of patients completed the 28-day assessment (or terminated the study early). The DSMC will make recommendations to the Steering Committee regarding the appropriateness of continuing the study following Stopping Guidelines in section 11.7 of this protocol.

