4.2.2 Primary Safety Endpoints

The primary safety endpoint is the number of SAEs and AEs during the 60-day study period.

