6.7.1 Permanent Suspension of Study Treatment

The investigator may permanently suspend the treatment in the following cases:

- If the patient's QTc interval is > 500 msec or an increase from baseline of > 60 msec is observed (please refer to section 9.2.3 for BBB correction);
- A DDI is identified with a concomitant medication that is medically required and cannot be resolved without the discontinuation of the study medication;

- If, in the view of the investigator, the patient experiences a severe allergic reaction that cannot be explained by the administration of any other medication;
- Development of liver function abnormality, as described in section 9.2.14.3.
- Development of an AE or any medical condition, which, in the opinion of the investigator, necessitates permanent suspension of study treatment;
- Withdrawal of consent.
- If the blind is broken (only allowed in emergency situations to determine appropriate patient care)

Patients have the right to discontinue study treatment for any reason. However, unless they withdraw consent and are no longer willing to participate, they should be followed for the remainder of the trial and all (S)AEs should be reported, regardless of whether or not the event is of CV origin or occurs under the care of another physician or institution.

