9.2.14 Management of AEs

9.2.14.1 AE Reporting

An AE is defined as any new untoward medical occurrence or worsening of a pre-existing medical condition in a patient or clinical investigation subject administered an investigational (medicinal) product and that does not necessarily have a causal relationship with this

treatment. An AE can therefore be any unfavorable and unintended sign (including an abnormal laboratory finding, for example), symptom, or disease temporally associated with the use of an investigational product, whether or not considered related to the investigational product.

AEs can be spontaneously reported or elicited during open-ended questioning, examination, or evaluation of a patient. (In order to prevent reporting bias, patients should not be questioned regarding the specific occurrence of one or more AEs.)

Any AE that results in any of the following outcomes will be considered an SAE:

1. Death
2. Life-threatening situation (Patient was at risk of death at the time of the event. This does not refer to an event that might have caused death if it was of greater intensity.)
3. New in-patient hospitalization or prolongation of existing index hospitalization
4. Persistent or significant disability or incapacity
5. Congenital anomaly or birth defect
6. Important medical events that may not result in death, be life-threatening, or require hospitalization but may jeopardize the patient and may require medical or surgical intervention to prevent one of the above outcomes (based upon appropriate medical judgment), e.g., allergic bronchospasm requiring intensive treatment in an emergency room or at home, blood dyscrasias or convulsions that do not result in in-patient hospitalization, or the development of drug dependency or drug abuse. Potential DILI is also considered an important medical event. (See Section 9.2.14.3 for the definition of potential DILI.)

The term “severe” is often used to describe the intensity (severity) of a specific event (as in mild, moderate, or severe pain); the event itself, however, may be of relatively minor medical significance (such as severe headache). By contrast, the term “serious” is used to describe an event based on an event outcome or actions usually associated with events that pose a threat to a patient’s life or functioning. Seriousness (not severity) serves as a guide for defining regulatory reporting obligations.

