12.6 Adjudication Committee

This Committee consists of at least three clinicians who have been appointed by the Steering Committee. The members of the Adjudication Committee will classify all SAEs to pre-specified definitions, as described in the Event Classification Manual, based on medical records and other documents. In addition, all endpoints will be verified by the Adjudication Committee.

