### **4.2.2 Safety Endpoints**

The primary safety endpoint is the number of Serious Adverse Events (SAEs) and Adverse events (AEs) which occur during the 60-day study period.

The secondary safety endpoints include changes in C-SSRS, blood chemistry and hematology parameters (including lymphocyte count), ALT, AST, bilirubin, eGFR, creatinine, INR and QTc interval from Electrocardiogram (ECG) recordings at 5 hours post morning dose during 28 days post randomization.

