### 9.3.8 Adverse Events

Adverse events are to be recorded throughout the study, beginning at the moment of informed consent. AEs will be coded using MedDRA and displayed in tables and listings by System Organ Class (SOC) and Preferred Term (PT).

Analyses of adverse events will be performed for those events that are considered treatment-emergent, where a treatment-emergent AE (TEAE) is defined as one that started, or worsened in severity or seriousness following the first dose of IMP. An AE with onset prior to the start of the administration of the first dose of study drug, or where the stop date is before the start of the administration of the first dose of study drug, or where the study drug was not started, will be considered as pre-study. In case the onset date is on the same day as the first dose of study drug and either the time of first dose or time of AE onset is missing, then AE is considered treatment-emergent.

AE intensity will be qualified as mild, moderate, or severe. Maximum severity will be assumed for an AE with missing severity. The relationship to the study drug will be qualified as related (including categories related, probably, possibly) or unrelated.

If the AE start date is missing or partial, the AE will be assigned to the appropriate period using available start date information and the stop date, if present as described above.

The following tables will be presented for AEs incidence and/or number of events will be reported as appropriate:

- Overall summary of AEs
- TEAEs by system organ class and preferred term
- Treatment related TEAEs by system organ class and preferred term
- Serious TEAEs by system organ class and preferred term
- TEAEs by system organ class, preferred term and maximum severity
- TEAEs leading to study drug discontinuation by system organ class and preferred term
- Listing of AEs
- Listing of Serious TEAEs
- Listing of AESIs
- Listing of Deaths

Adverse event incidence is counted only once per system organ class and once per preferred term. The number and percent of subjects experiencing events are reported. Outputs reported at maximum severity show the highest severity reported by a patient per system organ class and preferred term.

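### The primary safety endpoint counts the trial's own efficacy events, so a real benefit would offset non-endpoint drug harm in the pooled SAE and AE figures

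*Protocol*

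**What the plan says.** The definition appears three times, each time without an exclusion. The synopsis has "Number of serious adverse events (SAEs) and adverse events (AEs) during the 60-day study period in each group". Protocol 4.2.2 has "The primary safety endpoint is the number of SAEs and AEs during the 60-day study period". SAP 4.2.2 has "The primary safety endpoint is the number of Serious Adverse Events (SAEs) and Adverse events (AEs) which occur during the 60-day study period".

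Protocol 9.2.14.1 defines events without regard to cause: "An AE is defined as any new untoward medical occurrence or worsening of a pre-existing medical condition". On seriousness it says "Any AE that results in any of the following outcomes will be considered an SAE", and its list includes death, life-threatening situations, and new or prolonged hospitalization. Protocol 6.7.1, writing about patients who have stopped study treatment, asks that "all (S)AEs should be reported, regardless of whether or not the event is of CV origin".

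The primary efficacy composite (Protocol 4.1.2) covers death, ICU or ventilatory support, heart failure, myocardial infarction, myocarditis, arrhythmia and stroke to Day 28. That period lies inside the 60-day safety window.

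Protocol 12.6 and SAP 4.3 have a committee classify every SAE, and Protocol 12.6 adds that "all endpoints will be verified by the Adjudication Committee". Neither section uses the result to separate endpoint events from other safety events. SAP 9.3.8 lists an overall AE summary and tables such as "Serious TEAEs by system organ class and preferred term", all restricted to treatment-emergent events. It lists no table without endpoint events.

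**The concern.** Deaths, infarctions, strokes and similar events enter the trial twice: once as the outcome the drug is meant to reduce, and again as AEs or SAEs. The treatment-emergent restriction does not separate the two roles, because an endpoint event after the first dose is treatment-emergent.

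A reader comparing the pooled SAE figures between arms therefore sees benefit and toxicity netted against each other. Equal totals could mean no effect of any kind, or a real benefit together with a similar number of drug-caused events of other kinds. The offset grows with efficacy, so it is largest in the case where the balance of benefit and harm would matter most.

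**Working it through.** **Design figure.** Inputs from Protocol 11.1: 19% on placebo, 9.5% on CardiolRx, two-sided alpha 0.05, 80% power. The mean rate is 0.1425. With pooled variance under the null,

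n = [1.960·√(2·0.1425·0.8575) + 0.842·√(0.19·0.81 + 0.095·0.905)]² / 0.095² = 211.4.

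This is 212 when rounded up, and 211 per arm gives 79.9% power. The stated 211 reproduces.

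**Size of the benefit.** 211 × 0.19 = 40.1 and 211 × 0.095 = 20.0, so about 20 fewer patients on CardiolRx have a primary event.

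**Which of these are SAEs.** Death always is. Others need not be. Appendix 17.8.1 accepts new oxygen by mask or nasal cannula when saturation is below 94%. Appendix 17.8.5 accepts sinus bradycardia below 50/min, Mobitz I block, atrial fibrillation lasting 30 seconds, and more than 10 ventricular premature complexes a minute. Let s be the share of primary events that are serious. The documents do not give s, so a range is shown.

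**Hidden rise.** Let b be the placebo proportion with some other SAE. The documents do not give it either; 5% and 10% are assumptions. Take other SAEs as independent of primary events, and s as equal in both arms. The proportion with any SAE is level when

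(1 − 0.19s)(1 − b) = (1 − 0.095s)(1 − x),

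where x is the CardiolRx proportion with some other SAE. For b = 5% and s = 1, x = 1 − 0.81 × 0.95 / 0.905 = 15.0%, and both arms show 23.05% with any SAE. The extra patients are 211 × (x − b). The last column is the exact power of a two-sided 5% Fisher test of b against x, if other SAEs were compared alone.

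| b | s | any SAE, both arms | x | extra patients | power alone |
|---|---|---|---|---|---|
| 5% | 1 | 23.05% | 15.0% | 21 | 92% |
| 5% | 0.5 | 14.0% | 9.7% | 10 | 39% |
| 5% | 0.25 | 9.5% | 7.3% | 5 | 12% |
| 10% | 1 | 27.1% | 19.4% | 20 | 75% |
| 10% | 0.5 | 18.6% | 14.5% | 9 | 25% |

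**Count scale.** The endpoint is worded as a number of events, so the same check was made on counts, with one event per affected patient and s = 1. At b = 5%, placebo has 211 × (0.19 + 0.05) = 50.6 SAEs. CardiolRx with 9.5 extra drug-caused SAEs per 100 patients has 211 × (0.095 + 0.05 + 0.095) = 50.6. Without endpoint events the counts are 30.6 and 10.6, so z = 20.0/√41.2 = 3.12.

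**AE figure.** If patients average 1 to 5 AEs each (assumption), the 9.5-point benefit is 0.095/1 = 9.5% down to 0.095/5 = 1.9% of the AE count. The offset is still there but diluted.

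**The case against.** The strongest reply is that no conclusion rests on one pooled total. The documents attach no test, margin or decision rule to this endpoint. SAP 9.3.8 tabulates events by organ class and preferred term, drug-related events, and events leading to discontinuation, and it lists deaths and events of special interest. QTc and laboratory changes are separate secondary safety endpoints (Protocol 4.2.3). The DSMC reviews safety events by treatment code throughout (Protocol 12.5). All of this stands. A reader might infer that the trial would miss the harm, or would declare the drug safe because the totals match. The documents do not support that, because harm hidden in the pooled row could still appear in these outputs. They supplement the primary safety endpoint but do not correct it: an excess scattered over many terms may show in no single row, and the drug-related table depends on causality judgement.

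A reader might also treat every primary event as an SAE and quote only the 21-patient figure. Appendix 17.8 does not support that, which is why the size is given as a range.

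The third reply is that the trial stopped early and the SAP drops efficacy analysis and almost all testing (SAP 6.2, 9.1.1). This also stands. The calculation describes the full 422-patient design, and no offset arises without a real benefit. SAP 4.2.2 nevertheless keeps the definition unchanged, and SAP 2 says the plan is approved before unblinding.

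Finally, an all-event count is a defensible measure, and a line without endpoint events loses deaths and arrhythmias, some of which could be caused by the drug. That is a good reason not to let such a line replace the totals.

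**Conclusion.** The point holds for the pooled SAE and AE figures. As defined, the primary safety endpoint nets the intended benefit against non-endpoint harm, most clearly for SAEs. At the design rates with a 5% background, the concealed excess runs from about 5 to about 21 patients of 211 as the serious share of primary events goes from a quarter to all. The power to see that excess in a separate comparison runs from 12% to 92%, so separating the events helps most when most primary events are serious. These sizes rest on the planned 50% reduction being real, the assumed background rate, independence, and full enrolment. They describe masking in the headline safety figures, not in the safety evaluation as a whole. The change is worth making because it is cheap and removes the offset for non-endpoint events.

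**What to change.** In Protocol 4.2.2 and SAP 4.2.2 and 9.3.8, with the synopsis line matched, keep the all-SAE and all-AE totals. Beside them, with equal prominence, report for each arm the number and percent of patients with at least one SAE, and with at least one AE, other than an adjudicated primary-endpoint event, together with the number of such events. In the protocol's full-trial analysis, give a 95% confidence interval for the difference in proportions. In the abbreviated SAP, report the figures descriptively, in line with its rule against testing safety data.

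The cost is one extra table, built from the adjudication already planned in Protocol 12.6 and SAP 4.3, with no new data collection. The downside is that a drug-caused event of an endpoint type, such as an arrhythmia or a death, appears only in the totals. For that reason the totals stay and neither line leads.
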